5.3.3 Withdrawal

Subjects must be withdrawn from the trial (treatment and procedures) for the following reasons:

- Subject withdraws consent from study treatment and study procedures. A
 subject must be removed from the trial at his/her own request or at the request
 of his/her legally acceptable representative. At any time during the trial and
 without giving reasons, a subject may decline to participate further. The subject
 will not suffer any disadvantage as a result.
- Subject is lost to follow-up.
- Death.

Subjects may be withdrawn from the study for the following reasons:

- The subject is non-compliant with study drug, trial procedures, or both; including the use of anti-cancer therapy not prescribed by the study protocol.
- Pregnancy. Pregnancy will be reported as an SAE. (Note: subjects who have been withdrawn from treatment with study drug because of pregnancy should not undergo CT scans [with contrast]/MRI or bone scans while pregnant.)
- If, in the investigator's opinion, continuation of the trial would be harmful to the subject's well-being.
- Severe allergic reaction or unacceptable toxicity to both study drugs (see Section 6.9).
- The development of a second cancer.
- Development of an intercurrent illness or situation which would, in the judgment of the investigator, significantly affect assessments of clinical status and trial endpoints.
- Deterioration of ECOG performance status to greater than 2 despite best supportive care and attributed as at least possibly related to protocol therapy.
- Use of illicit drugs or other substances that may, in the opinion of the investigator, have a reasonable chance of contributing to toxicity or otherwise skewing trial result.

Administrative or safety reasons requiring study closure.

Any subject removed from the trial will remain under medical supervision until discharge or transfer is medically acceptable. In all cases, the reason for withdrawal must be recorded in the CRF and in the subject's medical records. Details for the premature termination of the study as a whole are provided in Section 10 (Premature termination of the study).

6. Treatments

6.1 Treatments to be administered

All patients will be treated with the combination of sorafenib plus nivolumab. Patients will be enrolled to one of two sequential cohorts: the Dose Escalation Cohort (Part 1) or the Child Pugh B Expansion Cohort (Part 2). Patients enrolled to the Dose Escalation Cohort (Part 1) will be enrolled starting at Dose Level -1 according to Table 6.2.1-1 below, following standard 3+3 dose escalation rules as outlined in Section 6.2.2 below. Patients enrolled to the Child Pugh B Expansion Cohort (Part 2) will be enrolled to the maximum tolerated dose (MTD) of sorafenib identified in Part 1 along with standard dose nivolumab, as described below in Section 6.2.2.

6.2 Part 1: Dose Escalation Cohort

Between 3-12 patients will be enrolled in Part 1 starting at Dose Level (DL) -1. See Table 6.2.1-1 for dose levels and Table 6.2.2-1 for dose escalation decision rules. Standard dose nivolumab 240 mg IV every 14 days will be used for both dose levels based upon absence of established dose-relationship for toxicities attributed to this agent in advanced HCC patients.⁴

6.2.1 Part 1 dose levels

Table 6.2.1-1. Part 1 Dose Levels

Drug	Dose Level -2	Dose Level -1 (starting dose)	Dose Level 1
	n =3-6 patients	n = 3-6 patients	n = 0-6 patients
Sorafenib	400 mg PO QOD	400 mg PO daily	400 mg PO BID
Nivolumab	240 mg IV Q2 weeks over 30 minutes		

6.2.2 3+3 dose escalation rules

Table 6.2.2-1. Dose Escalation Decision Rules

Number of Patients with DLT at a Given Dose Level	Escalation Decision Rule
0 out of 3	Dose escalate to next higher dose level. If already at DL 1, enroll 3 additional patients at DL 1.
≥ 2 out of 3*	Dose escalation will be stopped. This dose level will be declared the maximally administered dose (highest dose administered). The next lower cohort will be expanded to 6 patients. If no DLTs are seen consider an intermediate dose level between this dose and the MAD dose.
1 out of 3	Enter 3 more patients at this dose level.
	If 0 of these 3 patients experience a DLT, proceed to the next dose level. If already at DL 1, then DL 1 is the MTD.
	If 1 or more of these 3 patients suffer a DLT, then dose escalation is stopped, and this dose is declared the maximally administered dose.
≤ 1 out of 6 at highest dose level below the maximally administered dose	This is the MTD and recommended Expansion Cohort dose.

Note: Dose escalation will stop at Dose Level 1 which is the FDA-labeled dose of sorafenib as monotherapy for HCC. If >1 DLT occur at DL-2 a decision will be made whether to amend or terminate the study.

6.2.3 Dose limiting toxicity (DLT) window and definitions

The DLT window will be 28 days (1 cycle). Subjects must receive 2 doses of nivolumab and at least 75% of sorafenib doses within 28 days (1 cycle), or experience a qualifying DLT event, to be evaluable for DLT. DLT will be defined as clinically-significant toxicities which are at least possibly treatment-related and meet criteria listed in the sections below.

Toxicity will be graded by NCI CTCAE v.4.03 (https://ctep.cancer.gov/). Toxicity grade should be determined after standard, optimal supportive care treatments have been provided when appropriate. Optimal supportive care is defined as standard of care measures (such as electrolyte supplementation, the use of loperamide for diarrhea or antiemetics for nausea, or topical skin care for rash) that the treating physician deems appropriate and sustainable over multiple cycles of therapy. Clinically significant toxicity is defined as requiring therapeutic intervention beyond standard supportive care and/or placing the patient at risk for other toxicity by the judgment of the treating investigator.

After experiencing a DLT, a subject may resume treatment with dose reduction and/or optimal supportive care according to protocol guidance on dose modification and delay, once criteria for retreatment have been met and provided criteria for discontinuation have not been met.

6.2.3.1 **Hematologic DLT**

- Grade 4 hematologic toxicity (limited to neutrophil, hemoglobin, and platelet counts)
 Lymphopenia is excluded
- Prolonged Grade 3 thrombocytopenia > 7 days, requiring dose modifications during Cycle 1, requiring platelet transfusion, or associated with clinically relevant bleeding (as defined by bleeding requiring hospitalization, transfusion, or an invasive procedure such as endoscopy)

3. Grade 3 neutropenia with fever (ANC < 1000 and T \geq 38.5°C)

6.2.3.3 DLT exceptions

The following AE will not be considered DLT:

- 1. Asymptomatic Grade 3 non-hepatic laboratory values, with the following specifications:
 - a. Asymptomatic Grade 3 laboratory values are only considered DLT if determined treatment-related and clinically significant (e.g. requiring therapeutic intervention)
 - b. Liver function test abnormalities will be determined DLT according to DLT definitions in Section 6.2.3.

- 2. Grade 3 hypertension that resolves to ≤140/90 within 7 days of adjustment or addition of oral blood pressure medication(s)
- 3. Grade 3 HFSR attributed to sorafenib
- 4. Grade 3 infusion reactions which resolve within 6 hours of supportive therapy are not considered DLT but require nivolumab discontinuation (see Section 6.9)
- 5. Grade 3 fatigue
- 6. Toxicity attributed to hepatocellular carcinoma (e.g. AE due to mass effect, obstruction, or pain caused by tumor growth or new lesions)

6.3 Part 2: Child Pugh B Expansion Cohort

After identification of MTD for sorafenib in combination with standard dose nivolumab in Part 1, approximately 12 additional patients with liver function will be enrolled to the Child Pugh B Expansion Cohort on combination therapy with sorafenib at MTD from Part 1 (400 mg PO daily) and nivolumab 240 mg IV every 14 days both starting on C1D1.

6.3.1 Dose Levels for Part 2 Child Pugh B Expansion Cohort

Drug	Dose	Part 2 (n =12 patients)
Sorafenib	400 mg PO daily	Start on C1D1
Nivolumab	240 mg IV Q14 days*	Start on C1D1

^{*}Option to switch nivolumab dosing to 480 mg IV Q28 days on or after C4D1 (see Section 6.5.1) with Study Chair approval in eligible patients.

6.4 Sorafenib

Sorafenib (BAY 43-9006) is an oral multi-kinase inhibitor targeting both tumor cells and the tumor vasculature. The chemical name for sorafenib tosylate is 4

Chloro-3-trifluoromethyl-phenyl)-ureido] -phenoxy}-pyridine-2

carboxylic acid methylamide-4-methylbenzene-sulfonate, and its molecular weight is 637 daltons. The structure of sorafenib is depicted in Figure 6.4-1.

Sorafenib (as Nexavar[™]) is approved for use in multiple countries including the United States (US), the European Union (EU), and many other countries for multiple oncology indications including renal cell carcinoma, HCC, and differentiated thyroid cancer.

Figure 6.4-1: Structure of sorafenib (BAY 43-9006)

Structure of BAY 43-9006 tosylate (BAY 54-9085)

6.4.1 Sorafenib dosage and administration

Subjects will be instructed on the proper administration of sorafenib. Sorafenib tablets should be taken approximately 12 hours apart if assigned to BID dose level or approximately 24 hours apart if assigned to QD dose level, at approximately the same time(s) each day. Sorafenib tablets should be taken without food, at least 1 hour before or at least 2 hours after a meal, and with up to 240 mL (approximately 1 cup or 8 oz.) of water. Consumption of grapefruit and grapefruit juice should be avoided while receiving study drug.

6.4.1.1 Sorafenib missed doses

Missed doses of sorafenib should be taken as soon as the subject remembers. However, if it < 12 hours before next dose due, the missed dose should be skipped and the subject should take his/her next dose as scheduled. A double dose should not be administered to make up for missed individual doses.

6.4.2 Sorafenib drug supply and handling

For Part 1 of study, sorafenib tablets were obtained locally from commercial supplies with prescription from treating investigator, as a standard therapy for HCC. For Part 2 of study after amendment to restrict to Child Pugh B7-9 liver dysfunction, sorafenib tablets will be supplied by Bayer HealthCare. The 200-mg tablet formulation contains sorafenib tosylate and the excipients croscarmellose sodium, microcrystalline cellulose, hypromellose, sodium lauryl sulfate, and magnesium stearate. The tablets have a film coating comprised of hypromellose, polyethylene glycol, titanium dioxide, and red ferric oxide, which has no effect on the release rate of the active ingredient, sorafenib tosylate. The tablets are un-debossed, salmon colored, weigh approximately 350 mg each, and are 10 mm (millimeter) round in shape. Sorafenib tablets do not need to be protected from light. They are sufficiently stable with regard to light, oxidation, thermal stress, and hydrolytic degradation. The formulation is presented as an immediate release (IR) dosage form, i.e., the active ingredient is completely dissolved under in

vitro test conditions within a short period of time. Additional information on prepared drug storage and administration are available in the sorafenib Investigator Brochure.

6.5 Nivolumab

Nivolumab (also referred to as BMS-936558 or MDX1106) is a human monoclonal antibody (HuMAb; immunoglobulin G4 [IgG4]-S228P) that targets the programmed death-1 (PD-1) cluster of differentiation 279 (CD279) cell surface membrane receptor. PD-1 is a negative regulatory molecule expressed by activated T and B lymphocytes. Binding of PD-1 to its ligands, programmed death-ligands 1 (PD-L1) and 2 (PD-L2), results in the down-regulation of lymphocyte activation. Inhibition of the interaction between PD-1 and its ligands promotes immune responses and antigen-specific T-cell responses to both foreign antigens as well as self-antigens. Nivolumab is a soluble protein consisting of 4 polypeptide chains, which include 2 identical heavy chains and 2 identical light chains. Nivolumab is expressed in Chinese hamster ovary (CHO) cells and is produced using standard mammalian cell cultivation and chromatographic purification technologies. The clinical study product is a sterile solution for parenteral administration.

Nivolumab (as OPDIVO[™]) is approved for use in multiple countries including the United States (US, Dec-2014), the European Union (EU, Jun-2015), and Japan (Jul-2014) for multiple oncology indications. OPDIVO[™] is not approved for use in HCC as of 1 June 2017.

6.5.1 Nivolumab dosage and administration

Nivolumab 240 mg flat dose will be administered as an IV infusion over 30 minutes through a 0.2-micron to 1.2-micron pore size, low-protein binding (polyethersulfone membrane) in-line filter. It is not to be administered as an IV push or bolus injection. Nivolumab injection can be infused undiluted (10 mg/mL) or diluted with 0.9% Sodium Chloride Injection, USP or 5% Dextrose Injection, USP to protein concentrations as low as 0.35 mg/mL. During drug product preparation and handling, vigorous mixing or shaking is to be avoided. Nivolumab infusions are compatible with polyvinyl chloride (PVC) or polyolefin containers and infusion sets, and glass bottles. At the end of the infusion, the line should be flushed with a sufficient quantity of dextrose or normal saline.

For patients enrolled to Part 2, nivolumab may be switched to monthly infusion of 480 mg Q28 days on or after C4D1 with Study Chair approval in patients with investigator-assessed clinical benefit and without any uncontrolled or grade >2 immune-related toxicity, based upon established safety and efficacy of the monthly dosing regimen across tumor types.⁴⁴ A note to file will be placed in the subject's study chart to document Study Chair or designee approval.

6.5.1.1 Nivolumab schedule modifications and definition of delay

Subjects may be dosed no less than 12 days between nivolumab doses at 240 mg dose Q14 days, and no less than 24 days between nivolumab doses at 480 mg monthly dose. Subjects may be dosed up to 3 days (for Q14 day dosing) or 6 days (for Q28 day dosing) after the scheduled date if necessary. A dose given more than 3 or 6 days after the intended dose date will be considered a delay for each respective dosing interval. Subsequent dosing should be based on the actual date of administration of the previous dose of drug.

6.5.1.2 Nivolumab premedication

Premedication for nivolumab is not required unless a subject has experienced prior infusion reaction. See Section 6.8.2.2. In subjects who have experienced a prior infusion reaction (< Grade 3) and who are determined eligible for retreatment, the following prophylactic premedications are recommended: diphenhydramine 50 mg (or equivalent) and/or acetaminophen 325 to 1000 mg at least 30 minutes before additional nivolumab administrations. If necessary, corticosteroids (recommended dose: up to 25 mg of IV hydrocortisone or equivalent) may be used.

6.5.2 Nivolumab drug supply and handling

Nivolumab was supplied by Bristol-Myers Squibb to each study site for Part 1 and beginning of Part 2 patient enrollment. Starting after protocol amendment (version 4.0) requiring Child Pugh B7-9 liver dysfunction for eligibility to Part 2, nivolumab will be prescribed as a standard therapy option for patients with Child Pugh B liver dysfunction from commercial supplies and administered according to package insert instructions. Additional information on prepared drug storage and administration are available in the nivolumab Investigator Brochure and package insert.

6.6 Blinding

This is an open-label study. No blinding will be performed.

6.7 Dose modifications and delays

Toxicity will be assessed according to NCI CTCAE v.4.03 (https://ctep.cancer.gov/). Dose modifications, interruptions, and treatment discontinuation for one or both study drugs will be determined according to the system showing the greatest degree of toxicity and according to the treating investigator's assessment of cause of toxicity. Toxicity will be formally assessed at protocol-defined safety assessment time points well as by investigator review of weekly laboratory testing and, in the interim, by any unscheduled patient contact with the study team.

General principles of dose modification and delay are listed below:

• Optimal supportive care should be provided for all clinically relevant toxicities.

 See Section 6.8 for guidance on supportive care/rescue medications for specific toxicities.

- For any toxicity (regardless of grade), despite optimal supportive care, that is felt
 by the treating investigator to represent a risk to the patient's safety, additional
 dose reduction, treatment delay, and/or treatment discontinuation (beyond per
 protocol dose modifications) are permitted at the discretion of the treating
 investigator.
- Scheduled safety and tumor assessments for all subjects should continue as per protocol even if dosing is delayed.
 - Safety assessments may be required more often if treatment delay for toxicity.
- No dose re-escalation is permitted after dose reduction for toxicity.
- If a treatment-related toxicity requiring treatment delay has not recovered to ≤
 Grade 1 after treatment delay ≥ 6 weeks (42 days) for toxicity, treatment will be
 discontinued.
 - Exceptions allowing longer treatment delay up to approximately 12 weeks for recovery of treatment-related toxicity in subjects who have demonstrated previous treatment benefit (e.g. radiographic regression and/or clinical improvement such as reduced pain or tumor marker) are permitted with documented approval from Study Chair or designee.

6.7.1 Sorafenib dose modifications and delays for toxicity

Sorafenib doses will be delayed or reduced for clinically significant hematologic and non-hematologic toxicities that are determined to be related to sorafenib therapy according to the guidelines in the sections below, according to types of toxicity.

Sorafenib dose reduction will follow predefined dose levels in Table 6.2.1-1 in Section 6.2.1. Subjects requiring dose reduction at current dose should be treated at next lower dose level until Dose Level -2. If additional toxicity attributed to sorafenib occurs despite reduction to Dose Level -2, sorafenib will be discontinued.

Table 6.7.1-1	Sorafenib dose modifications and delays for hematologic toxicity
---------------	--

Toxicity	ANC (x 109/L)	Hemoglobin (g/dL)	Platelets (x 10 ⁹ /L)	Sorafenib
Grade 1	≥ 1.5	< LLN – 10.0	≥75	Treat on time No change
Grade 2	≥ 1.0 to < 1.5	< 10.0 - 8.0	≥ 50 to < 75	Treat on time No change
Grade 3	≥ 0.5 to < 1.0	< 8.0 – 6.5	≥ 25 to < 50	Treat on time Reduce by one dose level
Grade 4	< 0.5	Life-threatening consequence; urgent intervention indicated	<25	Discontinue from study

Febrile Neutropenia				Delay sorafenib until toxicity has resolved to Grade 2 or less; when sorafenib is restarted, reduce by one dose level
------------------------	--	--	--	---

Table 6.7.1-2: Sorafenib dose modifications and delays for non-hematologic toxicity

Grade	Dose interruption	Dose modification
Grade 0-2* (except for HFSR or diarrhea)	Treat on time	No change
Grade 2 HFSR* or diarrhea	1 st occurrence: Continue treatment with augmented HFSR skin care and/or antidiarrheal regimen If no improvement within 7 days or ≥ 2 nd occurrence: Interrupt until < Grade 2	Decrease one dose level
Grade 3	Interrupt until ≤ Grade 2	Decrease one dose level
Grade 4	Discontinue from study	Discontinue from study

^{*}See Table 6.8.1-1 and Sections 6.8.1.1 through 6.8.1.3 for HFSR, diarrhea, and HTN supportive care guidance.

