6.7.2.1 Criteria to resume nivolumab dosing after delay for toxicity

Subjects may resume treatment with a study drug after treatment hold for toxicity if the drug-related AE(s) resolve to Grade ≤ 1 or baseline within 6 weeks (42 days), with the following exceptions:

- 1. Subjects may resume treatment in the presence of Grade 2 fatigue.
- 2. Subjects who have not experienced a Grade 3 drug-related skin AE may resume treatment in the presence of Grade 2 skin toxicity.
- 3. Subjects with baseline Grade 1 AST, ALT, or total bilirubin who require dose delays for reasons other than a drug-related hepatic event may resume treatment in the presence of Grade 2 AST, ALT, or total bilirubin.
- 4. Subjects who require dose delays for drug-related elevations in AST, ALT, or total bilirubin may resume treatment when these values have returned to their baseline CTCAE Grade or normal, provided the criteria for unacceptable toxicity requiring permanent discontinuation are not met (Section 6.9).
- 5. Drug-related pulmonary toxicity, diarrhea, or colitis must have resolved to baseline before treatment is resumed.
- 6. Drug-related endocrinopathies adequately controlled with only physiologic hormone replacement are acceptable for resuming treatment.
- 7. A longer treatment delay up to approximately 12 weeks for recovery of treatment-related toxicity in subjects may be permitted in subjects who have demonstrated previous treatment benefit (e.g. radiographic regression and/or clinical improvement such as reduced pain or tumor marker), with approval from Study Chair or designee.

If the criteria to resume treatment are met, the subject should restart treatment at the next scheduled time point per protocol.

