6.9 Unacceptable toxicity requiring treatment discontinuation

If one study drug is discontinued for unacceptable toxicity, treatment with the other agent will also be discontinued.

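### In Table 6.7.1-2, grade 3 hand-foot skin reaction or diarrhea may restart sorafenib at grade 2, while persistent or repeat grade 2 of the same toxicity must wait for grade 0-1

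*Combined protocol and SAP*

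**What the plan says.** Section 6.7.1, Table 6.7.1-2, sets the sorafenib rules for non-hematologic toxicity.

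- Grades 0 to 2 are treated on time with no change, but HFSR and diarrhea are taken out of that row.
- Grade 2 HFSR or diarrhea has its own row. A first occurrence continues on treatment with stepped-up supportive care. With no improvement within 7 days, or on a second or later occurrence: "Interrupt until < Grade 2". The dose column shows a one-level decrease.
- Grade 3, for any non-hematologic toxicity: "Interrupt until ≤ Grade 2". The dose column again shows a one-level decrease. HFSR and diarrhea are not mentioned.

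Table 6.7.1-1 in the same section has a similar threshold for febrile neutropenia: "Delay sorafenib until toxicity has resolved to Grade 2 or less; when sorafenib is restarted, reduce by one dose level". At the bottom of the dose ladder, Section 6.7.1 adds: "If additional toxicity attributed to sorafenib occurs despite reduction to Dose Level -2, sorafenib will be discontinued". Section 6.9 adds: "If one study drug is discontinued for unacceptable toxicity, treatment with the other agent will also be discontinued".

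**The concern.** By removing HFSR and diarrhea from the row that treats on time, the table signals that continuing grade 2 of these toxicities is not always acceptable for dosing. The grade 3 row does not carry that caution forward. A patient whose grade 3 diarrhea has improved only to grade 2 may restart. A patient whose diarrhea never exceeded grade 2, but lasted more than 7 days or came back, must wait for grade 0 or 1.

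Two things are at stake. One is avoidable sorafenib exposure in a patient who still has grade 2 HFSR or diarrhea after a grade 3 event. The other is consistency, since two investigators could read different rows for the same patient and act differently. Part 2 patients have little room for a further decrease: they start at 400 mg daily (Section 6.3), which is Dose Level -1, so one decrease takes them to Dose Level -2, the lowest.

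**Working it through.** The plan states no figure on this point, so the check is a comparison of rules.

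**Step 1. The two rows side by side, for HFSR or diarrhea.**

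| | Grade 2, persistent or repeat | Grade 3 |
|---|---|---|
| Sorafenib held until | below grade 2 (grade 0-1) | grade 2 or below (grade 0-2) |
| Dose on restart | one level lower | one level lower |

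The thresholds differ by one grade, in the unexpected direction. The dose reduction is the same, so it does not compensate.

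**Step 2. Is this just a by-product of grading?** In part. A hold triggered at grade 2 can only end below grade 2, so that cell is not odd in itself. For most toxicities no conflict follows, because grade 2 is treated on time and restarting at grade 2 after grade 3 fits with that. For HFSR and diarrhea the table can itself require a hold at grade 2, so a restart at grade 2 may be a restart into a state that calls for a hold.

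**Step 3. Where the rows collide.** Take a patient with an earlier grade 2 episode who then has grade 3 diarrhea that improves to grade 2. The grade 3 row ends the hold. If the present grade 2 counts as a second or later occurrence, the grade 2 row requires a hold and lists a decrease. A patient with no earlier episode can meet the same conflict 7 days after restarting, if the grade 2 has not improved. The table does not say which row governs.

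**Step 4. Does other text resolve it?**
- The table footnote points to Sections 6.8.1.1 to 6.8.1.3, which give supportive care and no restart grade.
- Section 6.7 ends treatment when a toxicity has not recovered to ≤ "Grade 1 after treatment delay ≥ 6 weeks (42 days) for toxicity". That is a discontinuation limit, not a restart threshold.
- Section 6.7 also lets the investigator delay longer for any grade. This is allowed, not required.
- Section 6.9.1 deals with discontinuation only.
- Section 6.7.2.1 concerns nivolumab (see the objection).

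None of these sets a stricter sorafenib restart after grade 3 HFSR or diarrhea.

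**Step 5. How many patients could reach the grade 3 row?** As an assumption, take the grade 3 rates in the SHARP trial from Section 1.3.2: 8% for diarrhea and 8% for HFSR. The share with either then lies between 8% (full overlap) and 8% + 8% = 16% (no overlap).
- With 12 patients: 12 × 0.08 = 0.96 to 12 × 0.16 = 1.92 expected. The chance of at least one is 1 − 0.92^12 = 0.63 to 1 − 0.84^12 = 0.88.
- With 6 patients: 6 × 0.08 = 0.48 to 6 × 0.16 = 0.96 expected. The chance of at least one is 1 − 0.92^6 = 0.39 to 1 − 0.84^6 = 0.65.

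These figures count everyone who reaches grade 3. Only those restarted while still at grade 2 are affected, and the documents give nothing from which to estimate that share. The rates are also for sorafenib alone in Child-Pugh A patients. Part 2 starts at half the labeled 400 mg twice daily, which could lower them, and adds nivolumab, which could raise diarrhea.

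**The case against.** The best defense is that each hold in the table ends one grade below its trigger, with one dose level removed, and that febrile neutropenia follows the same pattern. The two patients also differ: one has grade 2 that failed to settle or came back, while the other is improving and restarts at a lower dose. The table accepts dosing at grade 2 in principle, because a first occurrence continues. This explains the general grade 3 row. It does not explain why these two toxicities, singled out at grade 2, lose that handling at grade 3.

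It is also fair that exposure is probably limited. If the grade 2 row applies after restart, residual grade 2 that does not improve is held again after 7 days, so the extra exposure is about a week at a reduced dose. That reading is likely but not written down. Section 6.7.2 separately delays nivolumab for drug-related grade 2 or higher diarrhea.

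Three stronger readings are tempting, and the documents do not support them.

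- *Section 6.7.2.1 contradicts the grade 3 row.* Its lead sentence reads "Subjects may resume treatment with a study drug after treatment hold for toxicity" and asks for grade 1 or baseline, and its list requires diarrhea to be back at baseline. But its heading refers to nivolumab, and the last sentence of Section 6.7.2 introduces the list as the criteria for resuming nivolumab. The wording is loose; it is not a competing sorafenib rule.
- *One or two of 12 patients would be harmed.* The 0.96 to 1.92 counts patients reaching grade 3, not patients restarted at grade 2.
- *Patients would lose both drugs.* That needs a restart at grade 2, then persistence or a counted repeat, then a decision that residual grade 2 is additional toxicity at Dose Level -2, and then a stop classed as unacceptable toxicity. The protocol does not say that residual grade 2 counts in this way.

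**Conclusion.** The point holds as a minor patient-safety and consistency correction. For HFSR and diarrhea, the grade 3 restart threshold is one CTCAE grade looser than the threshold for persistent or repeat grade 2, with the same one-level decrease, and the two rows can conflict during recovery from grade 3. The comparison rests only on the text of Table 6.7.1-2 and on the absence of any overriding sorafenib rule in Sections 6.7, 6.8.1 and 6.9.1.

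The size of the clinical effect is unknown, because the number of patients who would restart at grade 2 cannot be estimated from the documents. The Part 2 primary endpoint, the rate of treatment-related grade 3 or higher events, is unaffected: a patient with related grade 3 HFSR or diarrhea has already been counted before any restart decision arises. No sample size or interval in Section 8 changes.

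**What to change.** 1. In the grade 3 row of Table 6.7.1-2, add that for HFSR and diarrhea the instruction is "Interrupt until < Grade 2". Leave other grade 3 non-hematologic toxicities as they are.
2. Optionally, add a footnote that grade 2 HFSR or diarrhea passed through on the way down from grade 3 is the same episode, is not a repeat occurrence, and triggers no second decrease. The first change removes most of the conflict; the footnote prevents a second decrease from being taken during the hold.
3. As tidying only, name nivolumab in place of the general reference to a study drug in the lead sentence of Section 6.7.2.1.

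No visits, data items or patients are added. The change needs an amendment with PRC and IRB approval (Section 9.4) and Bayer's agreement (Section 12.1). This version is dated 03/09/2022 and accrual is due to close on 30 April 2022, 22 + 30 = 52 days later, so the benefit would fall mainly on patients still on treatment. The clinical cost is a somewhat longer sorafenib hold after grade 3 HFSR or diarrhea. A slow recovery could occasionally near the 42-day limit, which Section 6.7 allows to be extended to about 12 weeks, with Study Chair approval, for patients who have shown benefit. Since Section 6.7 already expects recovery to grade 1 or below by 42 days, the stricter restart threshold is in keeping with the rest of the plan.
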